8.1.3. Continued Access Period

- Continued access: begins after study completion and ends at the end of trial. During the continued access period, patients on study treatment who continue to experience clinical benefit and no undue risks may continue to receive study treatment until 1 of the criteria for discontinuation is met. The continued access period includes continued access follow-up.
- Continued access follow-up: begins the day after the patient and the investigator agree that the patient will no longer continue treatment in the continued access period and lasts approximately 30 days.

The continued access period will apply to this study only if at least 1 patient is still on investigational product when study completion occurs.

Patients receiving investigational product and experiencing ongoing clinical benefit and no undue risks may continue to receive investigational product in the continued access period until 1 of the criteria for discontinuation is met (Section [7.3](#)). Lilly will notify investigators when the continued access period begins. Patients must sign a new informed consent form (ICF) before continued access is provided.

Patients who are in short-term follow-up when the continued access period begins will continue in short-term follow-up until the 30-day short-term follow-up visit is completed. Long-term follow-up does not apply.

Patients who are in long-term follow-up when the continued access period begins will be discontinued from long-term follow-up.

During the continued access period, all AEs, SAEs, and investigational product exposure will be reported on the case report form (CRF). Patient diaries for drug administration will no longer be required in the continued access period.

Serious adverse events will also be reported to Lilly Global Patient Safety (see Section 10.3.1). In the event that an SAE occurs, Lilly may request additional information (such as local laboratory results, concomitant medications, and hospitalizations) in order to evaluate the reported SAE.

Investigators will perform any other standard procedures and tests needed to treat and evaluate patients; however, the choice and timing of the tests will be at the investigator's discretion. Lilly will not routinely collect the results of these assessments.

8.1.4. Study Completion and End of Trial

This study will be considered complete (that is, the scientific evaluation will be complete [study completion]) following the final analysis/evaluation of overall survival or after approximately **CCI** survival events have occurred. Investigators will continue to follow the study schedule for all patients until notified by Lilly that study completion has occurred. "End of trial" refers to the date of the last visit or last scheduled procedure for the last patient on study treatment.

The end of trial occurs after study completion and after the last patient has discontinued study treatment and completed any applicable continued access follow-up.

8.2. Discussion of Design and Control

CCI patients will be entered in order to randomly assign **CCI** patients to 1 of 3 treatment arms using a **CCI** allocation ratio in favor of the LY2157299 plus lomustine arm. A randomized, controlled design is being used in this study. Randomization minimizes systematic bias in the selection and assignment of patients to study therapy and provides justification for inferential statistical methods to be used on data from this study. The study will use dynamic randomization for the known influence factors, such as age, PS, and primary or secondary GB.

Using an appropriate concurrent control arm (which is lomustine in combination with placebo) enables direct statistical estimation of benefits and harms due to study therapy and minimizes bias in the assessment and interpretation of observed treatment effects. The rationale behind favoring the combination arm in the randomization is that this is the primary treatment of interest to compare with lomustine alone. However, since there was some evidence of activity in patients with GB in Study JBAH where LY2157299 was administered as a monotherapy, there is medical interest in getting more information in terms of efficacy and safety for LY2157299 monotherapy. Therefore, a monotherapy arm is also included.

Since OS is not affected by pseudoprogression evaluations, OS is a preferred primary endpoint over PFS. A Bayesian design can be used to leverage survival data for lomustine alone from

historical clinical trials in order to benefit from the **CCI** randomization of the combination arm relative to lomustine alone with the goal of increasing power over an otherwise similar design.

Glioblastoma is a heterogenous tumor entity and treatment effects may be influenced by MGMT methylation, IDH1 gene mutation status, or other genetic differences. Hence, to understand this influence on OS, all patients will be required to provide tumor tissue to determine the genetic make-up of the tumor and its impact on survival.

Poststudy treatment with bevacizumab may affect the OS. Collection of poststudy treatment will be limited to the first new regimen and any new subsequent therapy will not be collected.

Patients and investigators will be blinded to the administration of LY2157299 using a LY2157299-matched placebo. In contrast to the favorable toxicity profile of LY2157299, blinding of lomustine is difficult to ensure due to its well-characterized bone marrow toxicity. Given the other toxicity concerns, a blinding of lomustine is not warranted for this study.

If a patient can no longer tolerate lomustine therapy but the patient is benefitting from the treatment, the patient may continue LY2157299 or placebo treatment after approval by the Lilly Clinical Research Physician (CRP). Treatment may continue until disease progression or additional unacceptable toxicity occurs (see Section 9.4.1).

After the trial is completed, biomarker assessment of the tumor tissue will be used to determine whether treatment with LY2157299 had a particular impact on subtypes with a gene expression profile associated with TGF- β -associated signaling. This retrospective evaluation will help to identify a possible subgroup of patients that may respond to LY2157299 treatment, either alone or in combination with lomustine. Hence, the collection of tumor tissue is important to design future Phase 3 studies or to enrich potential responders in future GB studies. Because PK may be associated with toxicity, sparse population PK sampling is being implemented in this study. Finally, the health outcome measures are important for evaluating patient reported outcomes and are needed for future Phase 3 study designs.

9. Treatment

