10.1.2. Efficacy Assessments during the Postdiscontinuation Period

After patients have discontinued study treatment, they may receive additional anticancer therapy at the discretion of the investigator.

For those patients who discontinue study treatment without objectively measured progressive disease, the investigative sites will continue to monitor patients approximately every 60 days (± 14 days) to evaluate tumor response by the same method used at baseline and throughout the study, until objective progression or the patient starts a new anticancer therapy.

Once a patient has objective progression or starts a new anticancer therapy, they will be followed for OS approximately every 60 days (± 14 days) until death or study completion.

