12.2.4.2. Postdiscontinuation Regimens

Listings of patients reporting postdiscontinuation therapies will be provided.

Bevacizumab treatment after poststudy drug discontinuation will be listed and included in the OS analyses to detect any potential influence on OS.

Listings will include regimen number indicating which different therapies and/or types of therapies are included in the same regimen. The numbers and percentages of patients reporting postdiscontinuation regimens will be provided overall.

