6.9. Concomitant Therapy

All medications will be coded to the generic preferred name according to the current World Health Organization (WHO) drug dictionary. All concomitant medications listings will include both the term reported in CRF and the WHO dictionary term for enrolled patients in each arm and if concomitant medication use is due to adverse event (AE), the associated AE will also be listed.

Enzyme-inducing and non-enzyme inducing anti-epileptic drug treatments will be determined retrospectively and indicated in the listings.

Patients with concomitant steroid use will be listed separately by each arm. Dose information including total daily dose and any dose modification at the start of each cycle will be provided in this listing.

Surgery for palliative reasons and carried out prior to discontinuation from study treatment will be captured separately.

Anti-cancer systemic therapy, radiotherapy and surgery that occurs post discontinuation of study treatment is captured separately from concomitant medication as the existence of such therapies can lead to censoring of time to event endpoints. Patients that received post discontinuation therapies will be listed by treatment arms.

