6.10.3. Secondary Efficacy Analyses/Outcomes/Comparisons

A similar Bayesian analysis as described in [Section 6.10.1](#) will also be carried out to provide the hazard rates and ratios including 90% predictive intervals of the HR between LY2157299 monotherapy and lomustine plus placebo therapy and, between LY2157299 plus lomustine therapy and LY2157299 monotherapy.

Additional exploratory analyses using proportional hazards models to control for other factors may be performed, including, but not limited to, adding a covariate indicating the extent of lomustine exposure, PD marker assessment of the tumor tissue, the known influence factors, such as age, PS, and primary or secondary GB and whether patients had poststudy treatment with bevacizumab.

The following secondary efficacy parameters will be summarized for each treatment group:

- PFS distribution parameters and PFS rate
- ORR
- Disease control rate

Progression-free survival (PFS) and PFS rate will be summarized (at **CCI** [REDACTED]) using Kaplan-Meier estimates of the median survival times (including 95% CIs) to inform assumptions for use in future trial planning (Kaplan and Meier 1958). Estimates of HRs

between the 3 arms will also be provided using proportional hazards models. Additional exploratory analyses using proportional hazards models to control for other factors may be performed.

Overall response rate (ORR) and, additionally, disease control rate given the risk of pseudoprogression, will be estimated by dividing the total number of responders ([CR or PR]) or [(CR or PR or SD)] by number of randomly assigned patients in each treatment group. Exact 95% CIs for each treatment arm will also be provided.

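### Post-study therapy is collected for the first new regimen only, so the planned check of bevacizumab's influence on OS will miss bevacizumab given later

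*Protocol*

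**What the plan says.** Protocol 8.2 names the issue itself: "Poststudy treatment with bevacizumab may affect the OS". Its next sentence sets the limit on data: "Collection of poststudy treatment will be limited to the first new regimen and any new subsequent therapy will not be collected".

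Protocol 12.2.4.2 then makes a firm commitment: "Bevacizumab treatment after poststudy drug discontinuation will be listed and included in the OS analyses to detect any potential influence on OS". Protocol 12.2.7 and SAP 6.10.3 give that commitment a form, a covariate for "whether patients had poststudy treatment with bevacizumab". They place it in optional work: "Additional exploratory analyses using proportional hazards models to control for other factors may be performed".

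Two other places bear on what is captured. SAP 6.9 states that "Anti-cancer systemic therapy, radiotherapy and surgery that occurs post discontinuation of study treatment is captured separately from concomitant medication" and that these therapies will be listed by arm; it does not repeat the first-regimen limit. Protocol 12.2.4.2 adds that "Listings will include regimen number indicating which different therapies and/or types of therapies are included in the same regimen", which fits oddly with a record of only one regimen.

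After progression or a new therapy, Protocol 10.1.2 keeps sites in contact with patients: "they will be followed for OS approximately every 60 days". Neither document says how to code a patient whose later regimens were not collected, and neither mentions that bevacizumab use may be under-recorded.

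**The concern.** The covariate asks whether a patient ever had bevacizumab after the study. The data can only answer whether it was part of the first new regimen. A yes/no variable built from these data would by default count a later recipient as untreated, although no coding rule is stated.

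There is room for later regimens. In the two historical lomustine arms of Table JBAL.5.1, progression came early relative to death (figures under the working). Post-study treatment is left to the investigator (Protocol 10.1.2), and exclusion criterion [15] bars most prior first-line bevacizumab, so most patients could still receive it.

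Capture could also differ by arm. Criterion [14] excludes prior nitrosourea, so monotherapy patients leave study treatment without having had lomustine, which Protocol 5.3 describes as the most accepted second-line option. For them lomustine first and bevacizumab later is a plausible sequence. Patients in the other two arms have already had lomustine. At stake is the reading of the OS hazard ratios that involve monotherapy, which are secondary objectives. Protocol 8.1 wants them to show whether monotherapy is as active as lomustine.

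**Working it through.** The plan states no figure on this point to reproduce. Rates of post-study bevacizumab use, its sequence and its effect on OS are not given, so *p*, *s* and the bevacizumab HR below are assumptions shown over a range.

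**Room for later therapy** (Table JBAL.5.1, lomustine arms)
- Enzastaurin trial: median PFS 1.64 months, median OS 7.1 months. (7.1 − 1.64)/7.1 = 77%.
- Cediranib trial: median PFS 82 days, or 82/30.4 = 2.7 months; median OS 9.8 months. (9.8 − 2.7)/9.8 = 72%.

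A difference of medians is not a median post-progression survival, but it shows that much of OS falls after progression.

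**Hidden users among recorded non-users**

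Let *p* be the share ever given bevacizumab and *s* the share of those who had it in the first new regimen. Recorded use is *ps*. The share of recorded non-users who in fact received it is *p*(1 − *s*)/(1 − *ps*). For example, *p* = 0.4 and *s* = 0.5 give 0.20/0.80 = 25%.

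| *p* | *s* = 0.9 | 0.7 | 0.5 | 0.3 |
|---|---|---|---|---|
| 0.2 | 2% | 7% | 11% | 15% |
| 0.4 | 6% | 17% | 25% | 32% |
| 0.6 | 13% | 31% | 43% | 51% |

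**Apparent difference between arms when true use is equal**

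The false gap in recorded use is *p* times the difference in *s*:
- equal capture: 0 points
- *p* = 0.4, capture 60% v 70%: 0.4 × 0.1 = 4 points
- *p* = 0.2, capture 40% v 80%: 0.2 × 0.4 = 8 points
- *p* = 0.4, capture 40% v 80%: 0.4 × 0.4 = 16 points
- *p* = 0.6, capture 40% v 80%: 0.6 × 0.4 = 24 points

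**Effect on an adjusted OS hazard ratio**

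This was a large-sample Cox simulation with exponential survival, control median (7.1 + 9.8)/2 = 8.45 months (the protocol rounds to 8.5), a 24-month cut-off, true treatment HR 1.0 and 60,000 patients per fit. Bevacizumab was treated as a fixed attribute, to isolate misclassification from timing. The HR is for the first-named arm against the second. Null fits scattered by about 0.01.

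| True use | Capture | Bevacizumab HR | Crude HR | Adjusted, true data | Adjusted, recorded data |
|---|---|---|---|---|---|
| 40% v 40% | 50% v 50% | 0.6 | 0.99 | 0.99 | 0.99 |
| 40% v 40% | 50% v 50% | 0.8 | 1.00 | 1.00 | 1.00 |
| 40% v 40% | 40% v 80% | 0.6 | 1.00 | 1.00 | 0.92 |
| 40% v 40% | 40% v 80% | 0.8 | 1.00 | 1.00 | 0.97 |
| 40% v 40% | 30% v 90% | 0.6 | 0.99 | 0.99 | 0.89 |
| 40% v 40% | 30% v 90% | 0.8 | 1.00 | 1.00 | 0.95 |
| 60% v 30% | 70% v 70% | 0.6 | 0.87 | 1.02 | 0.94 |
| 60% v 30% | 40% v 80% | 0.6 | 0.87 | 1.01 | 0.86 |

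Three things follow.
- Equal capture leaves the treatment HR alone but dilutes the bevacizumab effect: at 50% capture a true 0.6 is estimated as 0.68, and 0.8 as 0.83.
- Unequal capture lets adjustment create a difference where there was none, in favour of the arm with poorer capture.
- Where true use differs, adjustment on the recorded variable removes about half the imbalance at 70% capture. It removes none in the last row, where recorded use is 0.6 × 0.4 = 0.3 × 0.8 = 24% in both arms.

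**The case against.** The strongest reply is that nothing decisive depends on this variable. The primary model (Protocol 12.2.6 and Attachment 10, SAP 6.10.1) has no bevacizumab term. The monotherapy hazard ratios come from a similar Bayesian analysis, also with no stated covariate. OS is followed whatever therapy comes later. The Cox model is optional, and the candidate covariates listed in SAP 6.17 do not include post-study bevacizumab. All of this stands, and it confines the point to a supporting check.

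A reader might also infer that under-capture differs between the arms of the primary comparison. The documents do not support that. Both arms receive lomustine, and patients and investigators are blinded to LY2157299 or placebo (Protocol 9.6). A difference could arise if the drug prolonged survival and so allowed more regimens, but that requires a treatment effect. Even for monotherapy, the lomustine-then-bevacizumab sequence is an inference: therapy is at the investigator's discretion, and Protocol 5.3 shows that bevacizumab approval differs by region.

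Finally, SAP 6.9 and the regimen numbers in Protocol 12.2.4.2 might be read as fuller capture. They do ensure that bevacizumab combined with another drug in the first new regimen is seen. They do not override an explicit statement that later therapy is not collected; at best the three places conflict.

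**Conclusion.** The point holds for the planned bevacizumab check. Followed as written, Protocol 8.2 yields a variable that cannot deliver what Protocol 12.2.4.2 commits to, and neither document acknowledges this. The primary OS result and its decision rule are unaffected.

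The size cannot be established. The 0.92 to 0.97 range rests on assumed 40% use in both arms, assumed capture of 40% v 80% and an assumed bevacizumab HR of 0.6 to 0.8. With equal capture the adjusted treatment HR stays near 1.0 and only the bevacizumab effect is diluted. Under-ascertainment follows directly from the text. Unequal capture is only a possibility, mainly for the monotherapy arm and hence for secondary comparisons. A reader might take it as settled that later recipients will be coded as untreated; that is the natural default, not a stated rule.

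**What to change.** - Amend Protocol 8.2 so that any post-study bevacizumab, in any regimen, is recorded as yes/no with its first start date at the existing survival contacts. Use this for the Protocol 12.2.4.2 listing.
- In any OS model, enter bevacizumab as a time-dependent covariate from its start date. Longer survivors have more chance to reach later regimens, so a fixed yes/no term would add immortal-time bias even with complete capture.
- Reconcile Protocol 8.2, Protocol 12.2.4.2 and SAP 6.9 on which regimens are collected.
- Where later use cannot be recovered, label the variable 'bevacizumab in first post-study regimen' and state the limitation in the SAP and study report.

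The cost is a short protocol change, two eCRF fields and slightly more site data entry, with no new visit or procedure. Some capture would be retrospective: the amended protocol carries approvals dated March 2015, after the planned last visit of August 2014 in the synopsis. Some start dates will be missing. The relabelling alone needs no new data.

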9.1. Treatments Administered

The following treatments will be administered in this study:

- LY2157299 Monotherapy:
 - LY2157299 300 mg/day, given orally as three 50-mg tablets BID for 14 days, followed by 14 days of rest, equaling a 28-day cycle.
- LY2157299 plus lomustine therapy:
 - The first lomustine dose will be given as 100 mg/m².
 - Remaining doses (starting with the second lomustine dose) are based on the investigator's discretion and will be given orally once every 6 weeks at 100 to 130 mg/m².
 - LY2157299 300 mg/day, given orally as three 50-mg tablets BID for 14 days, followed by 14 days of rest, equaling a 28-day cycle.
- Lomustine plus placebo therapy:
 - The first lomustine dose will be given as 100 mg/m².
 - Remaining doses (starting with the second lomustine dose) from 100 to 130 mg/m² are based on the investigator's discretion and will be given orally once every 6 weeks..
 - LY2157299 -matched placebo, given orally as 3 tablets BID for 14 days, followed by 14 days of rest, equaling a 28-day cycle.

Lomustine doses should be rounded to the lowest available capsule strength.

Weight is used to determine dose and should be assessed at each cycle, and dose should be recalculated for each cycle.

The investigator or his/her designee is responsible for the following:

- explaining the correct use of the drug(s) and planned duration of each individual's treatment to the patient/site personnel,
- verifying that instructions are followed properly,
- maintaining accurate records of study drug dispensing and collection,
- and returning all unused medication to Lilly or its designee at the end of the study.

Note: In some cases, sites may destroy the material if, during the investigator site selection, the evaluator has verified and documented that the site has appropriate facilities and written procedures to dispose clinical trial materials.

Patients will be instructed to contact the investigator as soon as possible if they have a complaint or problem with the study drug so that the situation can be assessed.

To be considered compliant, the minimum planned treatment of LY2157299 is 10 days and a maximum of 14 days per 28-day cycle and at least cc1% of the allocated LY2157299 prescribed dose has to be administered within each cycle.

9.2. Materials and Supplies

9.2.1. LY2157299

LY2157299 will be provided by Lilly. Clinical trial materials will be labeled according to the country's regulatory requirements.

LY2157299 will be supplied in blister packs or other appropriate packaging of uncoated, round, white tablets (eg, 10 and 50 mg or other appropriate dosage forms). All materials must be stored at room temperature within temperature range specified on the material label.

The tablet should remain in the blister pack until just prior to administration.

If a patient vomits within 30 minutes of taking a dose of LY2157299, the LY2157299 dose should be repeated 1 time only, that same day, if nausea/vomiting permits (at the discretion of the investigator). If a patient vomits within 30 minutes of taking both the morning and evening dose of LY2157299, the LY2157299 is repeated 1 time only on that day as described above.

LY2157299 should be taken at approximately the same time in the morning and evening every day. At this time LY2157299 has not been evaluated on whether food intake may change the PK profile. Hence, patients should take LY2157299 on an empty stomach preferably 2 hours before a meal. Patients should wait at least 1 hour after taking LY2157299 before eating a meal (see Section 9.4).

Tablets should be swallowed whole and not split, crushed, or dissolved for administration.

9.2.2. Lomustine

Lomustine will either be provided by Lilly in 10-, 40-, or 100-mg capsules in blisters or bottles or obtained as commercial preparation according to local requirements. At each visit, an appropriate number of capsules will be dispensed. The drug should be stored at room temperature. The size of lomustine capsules may differ between countries due to marketing availability.

